Falling during one-leg balance test: Participants could lose balance and fall during the one-leg balance test. To reduce the risk of falling during the one-leg balance test, research staff will place a gait belt around participants. For participants who use mobility aids, two research staff will perform the testing and additional steps such as placing a walker around the participant may also be employed.

Sleep disruption: It is possible that the one night of sleep apnea screening could disrupt sleep since participants would not be used to sleeping with sensors on their fingers and wrist. However, home sleep apnea testing is performed routinely in clinical practice and older adults are able to sleep for sufficient amount of time to make the test valid.

Skin irritation: The sensors worn for one night as part of the WatchPAT device the actigraph wrist band worn for 7 days may cause skin irritation or an allergy. We have extensive experience using wrist actigraphy and the WatchPat system, and have chosen these devices because they are well-tolerated by participants. They are also substantially less burdensome than other objective methods of recording sleep (i.e., requiring the participant to spend a night in a sleep laboratory). Research staff will carefully review with participants potential skin problems associated with wearing the wrist actigraph and the WatchPat sensors. Participants will be told to remove the device if they have any significant discomfort or any evidence of skin injury. Participants will have access to a research staff person, in case they have questions or concerns about the equipment. In addition, the company which makes the WatchPAT device has a 24-hour advice line that also provides troubleshooting support. Our monitoring devices are checked regularly to insure safe and proper operation. [name] (PI) will be notified immediately of any significant discomfort experienced by study participants.

Confidentiality and privacy breach: There is risk of breach of privacy via unintentional disclosure of Protected Health Information, which could lead to embarrassment and fraud, which in turn could have negative financial impact on participants. To ensure confidentiality of the research data collected, all participants will have a unique identification number assigned that is not based on any identifying information. This identification number will be used for all computer databases, which will be stored behind a UCLA network server, as well as for hard copy data collection forms. Access to these databases and hard copy forms will be limited to the study's approved research staff and will not be transmitted. Research hypnotic tracking logs (that use subject identification numbers) will be maintained to ensure that all of the hypnotics that are prepared, dispensed, and disposed (if unused) are accounted for at all times. These hypnotic tracking logs will be shared with the VA research

pharmacy (via a shared folder located behind a firewall). Consent forms and hard copies of data forms will be stored in locked file cabinets in locked offices with access limited to approved research staff. Electronic lists of names and contact information will be kept separate from other data in limited access folders on the UCLA secure server.

We will rent a United States Post Office Box, where participants may mail study documents if they are unable to drop off the document to our research office or meet our research staff to hand deliver the documents. Our research staff will transport the study documents directly from the US P.O. Box to the research office.

Risk/Benefit analysis

The risks of the study are no greater than the risks associated with current clinical protocols for discontinuation of a hypnotic. In fact, monitoring for side-effects will be more structured during the study than in clinical practice. Considering the study's potential to assist participants in reducing/discontinuing hypnotic use, the risk/benefit balance appears acceptable

Primary data analysis plan and power analyses

We will use an intention-to-treat approach for all analyses. We plan to randomize 188 individuals (including both UCLA and VA sites), of whom we expect 13% to drop out (i.e., fail to complete study assessments) by 6-months, yielding N=164 participants with complete data (~ 82 per group). *We base this drop-out on our completed study ([name] VA Merit 08-295)*. We will include terms for stratification characteristics in all of the models. All analyses below assume $\alpha=0.05$, power=0.80, and two-sided hypothesis tests. Effect sizes are in the measure's natural units and Cohen's d (large=.8; medium=.5; small=.2).

- ***H1: Dysfunctional Beliefs and Attitudes About Sleep – Medication Scale ratings will improve with MTcap compared to SGT+CBTI post-treatment and at 6 months follow-up:***

Analysis: We will fit a 2 (group) by 3 (time) mixed model analysis of variance (ANOVA) model. Interaction terms will be used to assess the change in DBAS medication item (from baseline→post-treatment, baseline→6 months) for MTcap vs. SGT+CBTI group. **Power Analysis:** Based upon our prior research, we estimate the correlation of DBAS scores from baseline to 6-months will be $r=0.55$ (95% CI=0.42-0.65) and the standard deviation will be 2.1. Assuming n=82 per group, the study could detect an effect of 0.9 units on the DBAS-16 scale (Cohen's $d=0.43$). If the baseline to follow-up correlation is $r=0.42$ (95% lower confidence limit [LCL]), the detectable effect size is 1.0 unit on the DBAS-16 scale (Cohen's $d=.47$).

- ***H2a: Participants who receive MTcap will have increased likelihood of hypnotic discontinuation post-treatment and at 6 months follow-up compared with those who receive SGT+CBTI:***

SGT+CBTI: The logistic regression models' dependent variable will be hypnotic discontinuation (yes=1/no=0 at post-treatment and 6-month follow-up) and the primary predictor of interest will be treatment group assignment (MTcap vs. SGT+CBTI). **Power Analysis:** We estimate that the SGT+CBTI group will have 60% discontinuation (based on prior studies = 59% to 63%, and our CBTI clinic's quality improvement data = 58% see "Technical Preliminary Studies"). We posit that a discontinuation percentage for the MTcap would need to be 80% (i.e., 20% greater) to be clinically meaningful. With an analytic sample size of n=82 per group, the study could detect a 20% difference in hypnotic discontinuation rate between groups (SGT+CBTI 60% vs. MTcap 80%). If the discontinuation rate of SGT+CBTI exceeds 60%, the study can detect even smaller differences (e.g., 17.8% difference if SGT+CBTI discontinuation rate is 70%). Even if the discontinuation percentage for the SGT+CBTI group is 50%, the study could detect a 21.3% difference (SGT+CBTI 50% vs. MTcap 71.3%). In our feasibility study, masked tapering resulted in 100% hypnotic discontinuation at post-treatment.

- ***H2b: Participants who receive MTcap will use less hypnotic post-treatment and at 6 months follow-up compared with those who receive SGT+CBTI:*** **Analysis:** Two outcomes will be

assessed: frequency (i.e., days used, 0 to 7) and quantity (i.e., average daily dose in diazepam milligram equivalents). For each outcome, we will fit a 2 (group) by 3 (time) mixed model analysis of variance (ANOVA). Interaction terms will be used to assess the change in the outcome (from baseline→post-treatment, baseline→6 months) for MTcap vs. SGT+CBTI. **Power Analysis:** For these calculations, we use statistics from our recent study, which found a baseline to 6-month correlation of $r=0.83$ (95% CI=0.77-0.88) and a standard deviation of 1.94 for a similar outcome measure—“days used of medications commonly used for insomnia” (days used, 0 to 7 days). Assuming $r=0.83$ and $n=82$ per group, we could detect a treatment effect of 0.5 ($d=0.26$) (i.e. a discontinuation rate of half a day more for MTcap vs. SGT+CBTI group). Assuming $r=0.77$ (i.e., using the LCL), we could detect a treatment effect of 0.6 days ($d=0.31$). If we disregard these prior data, power calculations still show that we could detect a treatment effect of Cohen's $d=.44$ with $n=82$ per group. For quantity of use, power calculations indicate that we could detect a treatment effect of $d=0.44$ with $n=82$ per group.

- ***H3: Insomnia Severity Index scores will be lower with MTcap compared to SGT+CBTI at 6 months follow-up.*** **Analysis:** Similar to H2, we will fit a mixed model ANOVA, and an interaction term will assess the change in ISI from baseline to 6 months for MTcap vs. SGT+CBTI. **Power Analysis:** Based on prior research, we found the standard deviation (SD) and “baseline-to-6 month follow-up” correlation of ISI scores to be $SD=5.3$ and $r=0.39$ (95% CI=0.24-0.52), respectively. Assuming $r=0.39$ with a sample size of $n=82$ per group, the study could detect an effect of 2.56 units on the ISI (or a Cohen's $d=0.48$). Assuming $r=0.24$ (i.e., using the LCL), we could detect an effect of 2.86 units on the ISI (or a Cohen's $d=0.54$). These power analyses suggest that the study could detect effects that are medium sized (i.e., $d=0.48$, $d=0.54$).

Exploratory data analysis plan: Using latent class analysis to identify group memberships based upon PHQ-9, GPM, ISI, and ESS measured at baseline, we will examine whether latent group membership moderates the strength of the treatment effect (i.e., examine if the MTcap treatment effect is stronger for particular latent class groups). To explore changes in cognition and balance, we will test whether MTcap improves Digit Symbol Substitution, MMSE, Trails A & B, & One-leg balance post-treatment and at 6-month follow-up, using mixed model ANOVA methods described above.

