Title: Sleep Without Insomnia or The Use of Chronic Hypnotics (SWITCH)

PI: [name], MSHS

NCT number: NCT03687086

Document date: June 19, 2020

SWITCH STUDY PROTOCOL (06.19.2020)

[APPENDIX: "Video/Telehealth Visit Addendum to SWITCH Study Protocol" is at end of document](#)

Design

This is a 5-year multi-site randomized controlled trial that will recruit participants from UCLA Health System and VA Greater Los Angeles.

Setting: To ensure that we meet enrollment targets, the study will include both VAGLA and UCLA Health System. At least 1,200 unique patients at VAGLA have the targeted hypnotics listed in their medical records for at least 3 months within the past 6 months, and 9,100 unique patients at UCLA Health System who receive primary or medicine subspecialty care in the northwest Los Angeles UCLA Health System outpatient clinics have the targeted medications listed within 12 months.

Inclusion/Exclusion criteria:

Inclusion criteria:

- Age > 55 years
- Use of lorazepam, alprazolam, temazepam, clonazepam and/or zolpidem for current or prior insomnia symptoms 2 or more nights per week for at least 3 months
- Current or prior insomnia symptoms
- Available to attend weekly in-person or video sessions over 9 weeks

Exclusion criteria:

High risk for complications in outpatient hypnotic discontinuation program:

- Seizure disorder
- Supratherapeutic or high baseline hypnotic dose (> diazepam-equivalent of 8 mg/night). Note that for individuals on > 1 of the targeted hypnotics, the total baseline hypnotic dose in diazepam-equivalents will be calculated and if > 8 mg/night, individual will be excluded.
- High baseline risk of complicated withdrawal; benzodiazepine intoxication or current or past symptoms of complicated benzodiazepine/alcohol withdrawal (e.g., seizure, delirium at baseline (prior to taper))
- Polydrug use (e.g., chronic high dose opioids)
- Unable to keep study medications in secure location
- Evidence of prescription fraud (e.g., multiple prescriptions for same drug filled at UCLA and non-UCLA pharmacies, diversion)

Discontinuation of hypnotic not appropriate:

- Study-targeted hypnotic used to treat another clinical condition (e.g., panic disorder)

Poor candidate for CBTI:

- Presence of bipolar disorder
- Cognitive impairment (e.g., Mini-Mental State Examination < 24)

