- Sleep/wake difficulty is better explained by another sleep disorder such as restless legs syndrome, narcolepsy, insufficient sleep syndrome, or circadian rhythm sleep-wake disorders
- Untreated sleep-disordered breathing (apnea-hypopnea index ≥ 30)
- Moderate sleep apnea (apnea-hypopnea index between 15-29.99) and daytime sleepiness (Epworth Sleepiness Scale score >10)
- Medically/psychiatrically unstable (e.g., planned major surgery during the study period; psychosis, suicidal, active alcohol/substance abuse based on history and medical records)
- Unstable housing situation

Recruitment

Recruitment will include a three-step screening process.

Step 1 (identification of participants): We will identify participants aged > 55 years who have current prescriptions for lorazepam, temazepam, alprazolam, clonazepam, and/or zolpidem (see “Hypnotics types” section below) for > 3 months. The sources we will use to identify these patients include: medication lists from electronic health records, and recruitment flyers.

A recruitment flyer with a cover memo to UCLA Health System providers will be distributed to providers in primary care, mental health, and sleep medicine clinics. The memo describes the study and basic eligibility criteria and asks the provider to share the flyer with appropriate patients. The flyer contains the study telephone number, so interested patients can call for more information.

Recruitment flyers also will be posted in approved areas of outpatient clinic waiting areas (as directed by clinic manager/administrator).

A recruitment letter and opt-out card will be mailed to patients identified from the electronic health record. Only authorized research staff will have access to the names of patients who will receive the mailing. Patients will be asked to return the opt-out card in a postage-paid envelope within 7 days of the letter mail date to indicate whether they wish to be called by our research staff. The letter will explain that research staff will call the patient if the opt-out card is not returned within the 7-day timeframe. The letter will also list the research office telephone number so patients can call to ask questions or indicate their willingness to participate.

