Individuals will be given the choice of having their study visits at UCLA or at either the VA West Los Angeles campus or the VA Sepulveda campus. This option allows individuals to choose the location that is most convenient for them. Individuals who express interest in a VA site will be informed that this choice entails following the VA Research and Development and VA IRB protocol, including signing VA forms, storage of their research data on VA servers and offices, and management of their study medications by VA staff. Individuals who choose to be seen at UCLA will follow the procedures described below. Those who choose to be seen at the VA will be enrolled in the VA study, and will no longer be considered UCLA study participants. Participants seen at the VA will sign a VA consent form and a VA HIPAA Authorization. In addition, they will be asked to sign a UCLA HIPAA Authorization for Research so VA study staff can assess their UCLA medical records to document medications and diagnoses.

In-person screening

Patients recruited directly by study staff in clinic will have the option to complete the screening process in-person with a member of the study team. Patients deemed eligible for participation will be offered to complete the in-person consenting process immediately following the in-person screening (see *in-person consent visit* below for additional information).

In-person consent visit

At the consent visit, potential participants will be shown the wrist actigraph and WatchPat monitoring equipment to ensure that they become familiar and comfortable with this equipment. Capacity to give informed consent will be evaluated with a brief questionnaire (Evaluation to Sign a Consent Form for Research) that asks the participant to recount major procedures and risks of the study. Participants who are unable to provide informed consent will be excluded; proxy consent will not be pursued. Participants who are able to provide informed consent will be asked to sign the written informed consent form and HIPAA authorization and will be provided with copies. A licensed study physician or nurse practitioner will perform the consent procedure.

-Preparation for consent visit:

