- Patients who request a copy of the consent and HIPAA authorization form prior to the consent visit will be sent copies of these documents via email, delivery (US Postal Service, FedEx, etc.), fax, or text, based upon patient preference. The address or number will be stored in the project database, REDCap.
- Prior to the consent visit, the study staff will review the UCLA electronic health record for study exclusion criteria and if the patient is ineligible, the patient will be contacted, and the in-person visit will be cancelled to avoid unnecessary in-person contact. We will not cancel consent visits for patients who indicate to our staff that the information obtained from the electronic health record is inaccurate.

Step 3 (in-person baseline assessment to determine remaining eligibility criteria: The purpose of the in-person visit will be to further explain the study, obtain written informed consent and begin the baseline assessment. After participants have provided written informed consent (in-person Visit 1), they will complete a baseline assessment that consists of 2 visits (each 45-60 minutes) to the study site.

- Questionnaires included in the baseline assessment:
 - Self-Administered Comorbidity Questionnaire, plus additional questions
 - Insomnia Severity Index (ISI)
 - Pittsburgh Sleep Quality Index (PSQI)
 - Dysfunctional Beliefs and Attitudes about Sleep – 16 item (DBAS-16)
 - Morningness Eveningness Questionnaire (MEQ)
 - Disturbing Dream/Nightmare Severity Index (DDNSI)
 - Restless Leg Syndrome questionnaire (RLS)
 - STOP-Bang questionnaire
 - Epworth Sleepiness Scale (ESS)
 - Brief Pain Inventory (BPI)
 - WHO Quality of Life -BREF (WHOQOL-BREF)
 - Mini-International Neuropsychiatric Interview (MINI) only for participants who have a history of bipolar disorder.
 - Primary Care Post Traumatic Stress Disorder (PC-PTSD)
 - Generalized Anxiety Disorder (GAD-7)
 - Patient Health Questionnaire-Depression Module (PHQ-9)
 - World Health Organization Alcohol, Smoking, and Substance Involvement Screening Test (WHO-ASSIST)
 - Trails A & B tests
 - Digit Symbol Substitution and Symbol Copy
 - Mini-Mental State Examination (MMSE)
 - One-leg standing balance
 - Benzodiazepine Dependence Questionnaire (BDEP)
 - Clinical Institute Withdrawal Assessment Scale – Benzodiazepines (CIWA-B)
 - Credibility/expectancy questionnaire (CEQ)
 - Demographic questions
 - Fall event question

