Participants with an apnea-hypopnea index ≥ 30 (from WatchPAT test) will not be eligible for randomization. Participants with an apnea-hypopnea index between 15 and 30 (moderate sleep apnea) and with daytime sleepiness (Epworth Sleepiness Scale score > 10) will also not be eligible for randomization. Participants with an apnea-hypopnea index between 15 and 30 and no daytime sleepiness will be eligible for randomization. We will inform participants with an apnea-hypopnea index > 15 that they may have sleep apnea and, with their permission, will inform their primary care, or other appropriate, provider.

A review of the participant’s medical record will be completed to assess for unstable medical or psychiatric conditions (e.g., new chemotherapy) that would make it difficult to maintain the participant’s engagement in the study. These individuals would also not be appropriate for CBTI under usual care conditions. Individuals excluded for unstable conditions will be reassessed 3 months later for eligibility, which is the process that would occur in a clinical setting. We will include individuals with stable psychiatric or medical conditions such as chronic pain or depression. Finally, we will notify the participant’s hypnotic prescriber at UCLA Health System (via encrypted email) about our intention to taper and discontinue the patient’s hypnotic in case there are undocumented clinical indications other than insomnia (see Email to Prescribers). If the prescribing physician does not agree with tapering the medication, the individual will not be randomized. Participants determined to be ineligible for the study will be notified by mail (see Participant Ineligibility Letter).

Randomization

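### The pre-randomisation prescriber notice is addressed only to UCLA prescribers, so a UCLA-site participant whose hypnotic is prescribed solely elsewhere misses it (low severity, cheap to fix)

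*Combined protocol and SAP*

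**What the plan says.** Under Eligibility determination for randomization, the study notifies the "hypnotic prescriber at UCLA Health System (via encrypted email) about our intention to taper and discontinue" the drug. The stated reason is that the drug may have an indication besides insomnia that is not on record. The next sentence bars randomisation if the prescribing physician objects; it does not mention UCLA. The mechanics are left to an attachment, Email to Prescribers, which is not part of the public document. The telehealth addendum leaves eligibility determination unchanged.

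The notice supports an exclusion criterion: "Study-targeted hypnotic used to treat another clinical condition (e.g., panic disorder").

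Entry does not depend on who prescribes:
- The inclusion criterion concerns use of one or more of five named drugs, "and/or zolpidem for current or prior insomnia symptoms 2 or more nights per week".
- Under Setting, the UCLA pool is patients who "have the targeted medications listed within 12 months".
- Under Recruitment, Step 1, the sources are "medication lists from electronic health records, and recruitment flyers".

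Under Step 3, the hypnotic medication log draws on the UCLA record and on a CURES query for prescriptions from outside UCLA.

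**The concern.** The notice is the last planned step before randomisation that asks the person who chose the drug whether tapering is appropriate, and the answer can stop entry. The protocol included it because it accepted that an indication might go unrecorded despite the earlier steps. A participant whose only prescriber is outside UCLA does not get that step. The reason is where the prescriber works, not any lower need for the check.

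What is at stake is safety and accuracy of eligibility. If the drug also treats another condition, and neither the participant, the record nor the eligibility meeting reveals it, someone the criteria mean to exclude could be tapered.

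**Working it through.** No arithmetic applies. The documents give no share of participants with an outside-only prescriber, so no rate can be computed. The check is to read the relevant provisions together.

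1. **Who is notified.** The eligibility section names the UCLA prescriber and an encrypted email route. The word *only* is an inference, but no other visible text sends a notice to an outside prescriber before randomisation. Under Care coordination at end of intervention period, primary care providers learn the final regimen, but that comes after the taper.

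2. **Whether an affected participant can enter.** No inclusion or exclusion criterion requires a UCLA prescriber. A drug listed in a UCLA record need not have been prescribed there, and a patient who responds to a flyer need not have a UCLA prescription either.

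3. **Whether the study would know.** The CURES query is made at baseline, so an outside prescription should be visible before the eligibility meeting. The plan gives no instruction to act on it by contacting that prescriber.

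4. **Whether the general objection rule closes the gap.** It refers to the prescribing physician without limit. A prescriber who is not told of the taper has no planned occasion to object.

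5. **What other checks cover the indication.**
 - The inclusion criterion ties use to insomnia symptoms, and use for another condition is an exclusion.
 - Before the consent visit, "the study staff will review the UCLA electronic health record for study exclusion criteria". That record may say less about an outside clinician's reason for prescribing. This is an inference; the documents do not describe its content.
 - "A licensed study physician or nurse practitioner will perform the consent procedure".
 - The baseline battery includes the "Self-Administered Comorbidity Questionnaire, plus additional questions", anxiety, PTSD and depression scales, and diagnostic questions for insomnia. No listed instrument is named for panic disorder, the exclusion's own example, and the MINI is given only where there is a history of bipolar disorder. The additional questions are not shown and might cover it.
 - At least one physician and one sleep psychologist attend the eligibility meeting.
 - Weekly CIWA-B and vital signs look for withdrawal once tapering has started. They do not establish the indication.

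6. **Effect on the comparison.** Eligibility is settled before the next allocation envelope is opened, so the gap applies equally to both arms. Sample size, alpha and the analysis models do not depend on it.

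Two groups fall outside the point. Those who choose a VA site enrol in the VA study under its own protocol. Those with both a UCLA and an outside prescriber already trigger the UCLA notice.

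**The case against.** The strongest reply is that the sentence describes the usual route for a cohort recruited through UCLA records, providers and clinics, that the objection rule is general, and that the unseen attachment may reach outside prescribers. On that view only a wording change is needed. The attachment cannot be checked. If it does reach them, the protocol sentence should still be aligned with it, because as written it names one recipient.

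A second reply is that harm needs a long chain: an outside-only prescriber, a second indication, and failure of every check listed above. Other provisions limit the damage if someone slips through: the cap of 8 mg diazepam-equivalent per night, the seizure and complicated-withdrawal exclusions, and extension of the taper up to 16 weeks. The medical record review at eligibility determination is not worded as UCLA-only, although its stated purpose is to find unstable conditions. All of this stands, and it is why the point is minor.

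A reader might infer from the CURES query that outside-only prescribing is common. The documents do not support that. The query also serves the prescription-fraud exclusion and follow-up of hypnotic use. It shows that outside prescriptions would be visible, not that they are frequent. Nor should a reader infer that these participants are tapered with no check on indication, or that UCLA prescribers are sure to answer. The protocol does not expressly require a reply from anyone, so what is lost is a chance to object.

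**Conclusion.** The point holds at low severity. Followed as written, the plan lets a UCLA-site participant whose targeted hypnotic is prescribed only outside UCLA be tapered without the notice that could have stopped randomisation. This is a stated rule with too narrow a scope, not an omitted detail.

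The number affected is unknown. It is probably small, because recruitment runs mainly through UCLA records and clinics. No risk or prevalence figure can be given. The conclusion rests on two assumptions: that such participants do enter, which the criteria permit but no count confirms, and that the attachment does not already extend the notice.

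**What to change.** In Eligibility determination for randomization, change the recipient to:

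*the participant's hypnotic prescriber(s), at UCLA Health System by encrypted email or, where the targeted hypnotic is prescribed outside UCLA (identified from the UCLA record, CURES or the participant), by secure fax or letter with the participant's permission.*

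Keep the rule that a prescriber who does not agree stops randomisation. Add one fallback: if the participant refuses permission, or the outside prescriber cannot be reached, the study physician asks the participant about the indication and documents the answer at the eligibility meeting.

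Do not add a rule that silence from a UCLA prescriber allows randomisation to proceed. The protocol is silent on non-reply, and such a rule could weaken the existing check for the main group. Changing the end-of-intervention notice would not help either, since it comes too late to affect eligibility.

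There is a precedent in the same section: with permission, sleep apnea findings go to the primary care or another suitable provider, with no limit to UCLA. The prescription data are already collected at baseline.

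The cost is a few letters or faxes, a short wait for affected participants, a possible change to the permission form (the HIPAA text is not shown, so it may already suffice), and possibly a few more exclusions.
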